7.1 Full Analysis Set (FAS)

The FAS will include all randomised patients according to their randomised treatment. However, some randomised patients will be excluded from the FAS, as decided during the Blind Review Meeting(s). A list of these patients can be found in the report of this meeting.

The FAS will be used for the evaluation of all efficacy and safety endpoints.

7.2 Safety Set (SS)

No separate Safety Set will be defined.

The FAS will be used for the evaluation of all safety parameters.

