All analyses will be adjusted for study site if feasible. No adjustment will be considered for binary outcomes (or time-to-event outcomes) when a low number of events yields computational problems.

12 Stratification Factors

Randomization was stratified for study site. Therefore, all models that are used for the estimation of treatment effects will be adjusted for study site.

13 Multiple Comparisons

Since only 1 primary endpoint is defined, no adjustment of the significance level is required.

For secondary efficacy endpoints, due to the exploratory nature of the efficacy analyses, no adjustment for multiple comparisons will be made.

14 Planned Subgroups, Interactions and Covariates

Moderator analyses will be performed for the primary outcome.

It will be verified if the treatment effect depends on the following baseline variables:

- baseline SOFA
- baseline NEWS score

For the baseline SOFA score, subgroups will be defined (<6 vs ≥ 6). Appropriate summary statistics per treatment arm and estimated treatment effects will be presented for each subgroup. In addition, the interaction between the above subgroups and treatment effect will be tested to assess whether the treatment effect differs according to subgroup.

The baseline NEWS score will be evaluated as a continuous moderator by including the main effect of the baseline NEWS score and the interaction between the baseline NEWS score and the treatment effect in the analysis model, allowing non-linearity for the relation of the baseline NEWS score (using restricted cubic splines with 4 knots).

Subgroup analyses will only be performed for the FAS.

15 Disposition of Study Subjects

A summary by treatment group will be provided for the following:

- Number of randomized subjects,
- Number treated according to randomization
- Number in Full Analysis Set (FAS)
- Number in Per Protocol Set (PPS)
- Exclusions from FAS
- Exclusions from PPS
- Number of subjects who died in hospital up to Day 5
- Number of subjects who were discharged up to Day 5

16 Demographics and Other Baseline Characteristics

All data recorded at baseline will be summarized by treatment group. Since it is a randomised study, no statistical tests will be performed to compare these data between the groups.

Summaries will be presented for FAS and PPS separately.

The following baseline information will be presented:

- Age, (y)
- Sex
- Weight (kg)
- NEWS score at ED presentation

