17.2.12 Return to work

For patients who were at work before inclusion in the study, the time until return to work will be compared. Patients lost-to-FU and patients not returned to work (at three months) are censored. Deceased patients are treated as a competing risk. The comparison will be based on a stratified Gray's test.

18 Adverse Events

The number of events and the number of patients experiencing adverse events will be summarized by treatment group.

Separate summaries will be presented for:

- Serious adverse events
- Serious or severe adverse events
- Treatment-related adverse events
- Treatment-related serious adverse events.

Summaries of adverse events will be presented only for the FAS.

19 Other Data

All other data will be summarized by treatment group and, if applicable, by day.

20 References

- Liang K-Y, Zeger SL. Indian Statistical Institute Longitudinal Data Analysis of Continuous and Discrete Responses for Pre-Post Designs. *Indian J Stat Ser B Ser B Biostat.* 2000;62(1):134-148. doi:10.2307/25053123
- SAS software, version 9.4 of the SAS System for Windows. Copyright © 2002 SAS Institute Inc. SAS and all other SAS Institute Inc. product or service names are registered trademarks or trademarks of SAS Institute Inc., Cary, NC, USA
- Stroup, W. Mixed model procedures to assess power, precision, and sample size in the design of experiments. *Proc. Biopharmaceutical Section. Am. Stat. Assoc., Baltimore, MD 15-24 (1999).*

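### The only adverse-event population is a FAS that drops some randomised patients on an unstated criterion and follows the randomised arm; no dosed, as-treated Safety Set exists

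*SAP*

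**What the plan says.** Four sections of the SAP settle which patients enter the safety analysis.

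- **Section 7.1** starts from everyone randomised, by assigned arm: "The FAS will include all randomised patients according to their randomised treatment". It then qualifies this: "However, some randomised patients will be excluded from the FAS, as decided during the Blind Review Meeting(s". No criterion, number or dosing status is given; the list of patients is in the meeting report. The section also gives the set both roles: "The FAS will be used for the evaluation of all efficacy and safety endpoints".
- **Section 7.2** is explicit: "No separate Safety Set will be defined". It then names the FAS as the safety population: "The FAS will be used for the evaluation of all safety parameters".
- **Section 15** plans disposition counts by treatment group, including "Number treated according to randomization" and the exclusions from the FAS.
- **Section 18** closes the question: "Summaries of adverse events will be presented only for the FAS".

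Section 7.3 also bears on this. It removes FAS patients from the Per Protocol Set if they missed every planned dose on day 1. Such patients can therefore be in the FAS.

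**The concern.** A safety table should describe everyone who was exposed, under the treatment they actually received. The FAS is built for efficacy and does neither by construction. Patients can leave it for reasons the SAP does not state, nothing confines those exclusions to undosed patients, and those who remain are classified by assignment rather than exposure.

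At stake is whether the reported adverse-event counts are complete and correctly attributed. This matters most for uncommon serious events, where one patient can change the reported rate visibly. It is not a detail left to the protocol: the SAP takes up the Safety Set under its own heading and decides against one.

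**Working it through.** The SAP states no figure that this point could reproduce. The check is a reading of the sections together, followed by illustrations on assumed counts.

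**Reading the rule through**

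1. *Dosed, then excluded from the FAS.* Section 7.1 removes the patient, Section 7.2 offers no other safety population, and Section 18 allows summaries in the FAS only. The patient appears in no Section 18 summary. Section 15 counts the exclusion, but the SAP specifies no adverse-event listing to go with it.
2. *Treated with the other arm's product.* Section 7.1 keeps the patient in the randomised arm. No as-treated summary is specified, so the events are counted in the arm not received.
3. *Never dosed.* Missing all planned day-1 doses leads to removal from the Per Protocol Set only. Unless Blind Review excluded the patient for another reason, a never-dosed patient stays in the FAS and so in the safety denominator.

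**Inputs for the illustrations**

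- From Section 3: 300 patients, 1:1, so 300 / 2 = 150 per arm.
- Assumed, because the SAP gives none: the number of patients affected (1, 3, 5 or 10), an event with 3 cases in 150, and true event risks of 20% and 10%.

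**Exclusion of dosed patients.** The share of one arm lost from the tables is k/150. For a single exclusion, starting from 3/150 = 2.0%:

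- the excluded patient had the event: 2/149 = 1.3%;
- the excluded patient did not: 3/149 = 2.0%.

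**Cross-treatment.** If k of 150 in each arm receive the other treatment, with f = k/150, the arms show 20(1 − f) + 10f and 10(1 − f) + 20f per cent. The observed difference is 10 × (1 − 2k/150) points.

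| k | Share of one arm lost if k dosed patients are excluded | Observed difference if k per arm are cross-treated (true 10 points) |
|---|---|---|
| 1 | 1/150 = 0.7% | 10 × (1 − 2/150) = 9.9 |
| 3 | 3/150 = 2.0% | 10 × (1 − 6/150) = 9.6 |
| 5 | 5/150 = 3.3% | 10 × (1 − 10/150) = 9.3 |
| 10 | 10/150 = 6.7% | 10 × (1 − 20/150) = 8.7 |

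**Undosed patients.** If u of 150 in the active arm were never dosed and carry only the background risk, a true excess of 10 points shows as 10 × (1 − u/150). For u = 3 this is 9.8 points.

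**Direction.** Cross-treatment and undosed patients pull the contrast towards zero. Exclusion of dosed patients has no fixed direction: it depends on the arm they were in and whether they had events.

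**The case against.** The strongest reply is that the harm is conditional and may not exist. The SAP does not say that any excluded patient was dosed or that anyone received the wrong treatment. It is dated 23 November 2023, after the Blind Review Meetings of 25 September and 23 October 2023, and Section 8.3 already gives a FAS count for one site. Its authors may have known that a separate set would hardly differ from the FAS. This is a fair inference, but the SAP does not say so, and the rule as written does not depend on it.

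Three stronger readings are tempting and not supported:

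- *Cross-treatment is foreseen or occurred.* The Section 15 row on treatment as randomised is a routine disposition count, and untreated patients also fall outside it. The Per Protocol criteria cover late and missed doses, not wrong treatment.
- *Exclusions bias the safety comparison towards no difference.* Section 5.3 keeps attendees blind to treatment, and exclusions can move the contrast either way or not at all.
- *Every exclusion hides events.* That would require each excluded patient to have been dosed and to have had an event. The SAP shows neither.

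There are partial safeguards. Exclusions will be tabulated by treatment group, and the DSMB review of safety data in Section 5.1 is not limited to the FAS. The plan tabulates adverse events without testing them, so no formal inference is at risk. These points limit the weight of the concern. They do not put an excluded patient's events into any Section 18 summary, and blinding does not restore lost data.

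**Conclusion.** The point stands as a defect in the stated rule, of unknown and possibly zero size. The SAP chooses an efficacy population with undefined exclusions, classified by assignment, as the sole basis for adverse-event reporting, and nothing elsewhere in the document reverses that choice.

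On the assumed counts the effect on a common event is small: with one to ten cross-treated patients per arm, a 10-point difference still shows as 9.9 to 8.7 points. A rare event is more sensitive, since one lost case among three takes 2.0% to 1.3%. These figures rest on 150 per arm and on assumed numbers of affected patients; they do not estimate what happened in the trial. The change should be made because the present rule cannot guarantee complete and correctly attributed safety reporting, and the alternative costs little.

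**What to change.** 1. In Section 7.2, replace "No separate Safety Set will be defined" with a Safety Set of all randomised patients who received at least one (partial) dose of study medication, analysed by treatment received.
2. Use this set for every summary in Section 18, and align the safety wording in Sections 7.1, 7.2 and 18.
3. List any adverse events of dosed patients who were excluded from the FAS, so that their absence from the efficacy set does not remove them from safety reporting.

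The cost is one population flag and SAP wording. The Per Protocol criteria in Section 7.3 already require dosing information for FAS patients. The SAP does not say whether dosing and adverse-event data are held for the excluded patients; if they are not, the report should say so. If no excluded patient was dosed, nobody was cross-treated and everyone in the FAS received a dose, the new set equals the FAS and the tables do not change.

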7.3 Per Protocol Set (PPS)

The Per Protocol Set will be reviewed and finalized prior to database lock at the Blind Review Meeting.

As decided during the Blind Review Meetings (September 25, 2023 and October 23, 2023) patients from the FAS with the following protocol deviations will be excluded from the per protocol set (PPS):

- Patients with 7 hours or more between hospital admission and first administration of study medication.
- Two or more successive doses missed due to other reasons than early discharge or death. If exact timing of missed doses is not available, patients with two doses missing on the same day.
- All planned doses missing on the first day (note that depending on the hour of randomisation, the number of planned doses might be one).

The PPS will be used for the evaluation of all efficacy endpoints.

8 General Issues for Statistical Analysis

8.1 Analysis Software

All analyses will be performed using SAS software, version 9.4 of the SAS System for Windows. Copyright © 2002 SAS Institute Inc. SAS and all other SAS Institute Inc. product or service names are registered trademarks or trademarks of SAS Institute Inc., Cary, NC, USA

8.2 Summary Statistics

Continuous variables will be summarized by treatment group by the number of non-missing data points, mean, standard deviation, median and interquartile range.

Categorical and ordinal variables will be summarized by treatment group by observed frequencies and percentages relative to the total number of non-missing items.

All summary statistics will be presented by treatment group and, where relevant, overall.

Day 1 is defined as the day of randomization.

8.3 Centre Effect

All statistical analyses of the outcomes of interest will be adjusted for study site. When applying the adjustment, the small site ULB Erasme (3 patients in the FAS) will be combined with UZ Brussels (Jette), as decided during the Blind review meeting (September 25, 2023).

9 Methods for Missing Data

In the statistical analyses of the longitudinally measured outcomes the presence of missing values is handled using a direct likelihood approach to fit the multivariate models. As such, the analysis is valid under the missing at random assumption (MAR).

Handling missing data for the SOFA score

In some settings, the following rules for single imputation will be used to handle missing SOFA scores or missing components for the calculation of the SOFA score.

- Patients who die within the time period of 5 days receive the worst outcome (highest SOFA score being equal to 24) starting at the day of death (even if a SOFA score is available at the day of death).
- SOFA scores are considered missing after the day of discharge
- If the patient's status does not require a lab analysis (due to good condition of the patient), missing data occur as per protocol. In this case the best possible score will be used for the SOFA score calculation (i.e. 0 points for bilirubin, blood platelets and creatinin) in the daily follow-up.
- If however a lab analysis was not ordered but was required as per protocol, the SOFA score of that day will be considered as missing.
- If a lab analysis was required, but one of the three lab values needed in the SOFA score was missing, the previous lab value was used for the calculation of the SOFA score. This was deemed appropriate, since it can be assumed that the specific lab parameter was not ordered that day because the function was considered stable. In rare cases where this happened at d1, the value of d2 will be used for the calculation of the SOFA score.

Frequency tables will be reported for the various settings where above imputation rules were applied.

For the analysis of the maximal SOFA score a multiple imputation approach will be used (cfr infra for details of the imputation model).

10 Data Transformations

An inverse hyperbolic sign transformation will be applied in the analysis of the (maximal) SOFA to obtain a more symmetric distribution of the model residuals. Analyses on untransformed scores will be reported as sensitivity analyses.

11 Multicenter Study

All analyses will be adjusted for study site if feasible. No adjustment will be considered for binary outcomes (or time-to-event outcomes) when a low number of events yields computational problems.

12 Stratification Factors

Randomization was stratified for study site. Therefore, all models that are used for the estimation of treatment effects will be adjusted for study site.

13 Multiple Comparisons

Since only 1 primary endpoint is defined, no adjustment of the significance level is required.

For secondary efficacy endpoints, due to the exploratory nature of the efficacy analyses, no adjustment for multiple comparisons will be made.

14 Planned Subgroups, Interactions and Covariates

Moderator analyses will be performed for the primary outcome.

It will be verified if the treatment effect depends on the following baseline variables:

- baseline SOFA
- baseline NEWS score

For the baseline SOFA score, subgroups will be defined (<6 vs ≥ 6). Appropriate summary statistics per treatment arm and estimated treatment effects will be presented for each subgroup. In addition, the interaction between the above subgroups and treatment effect will be tested to assess whether the treatment effect differs according to subgroup.

The baseline NEWS score will be evaluated as a continuous moderator by including the main effect of the baseline NEWS score and the interaction between the baseline NEWS score and the treatment effect in the analysis model, allowing non-linearity for the relation of the baseline NEWS score (using restricted cubic splines with 4 knots).

Subgroup analyses will only be performed for the FAS.

15 Disposition of Study Subjects

A summary by treatment group will be provided for the following:

- Number of randomized subjects,
- Number treated according to randomization
- Number in Full Analysis Set (FAS)
- Number in Per Protocol Set (PPS)
- Exclusions from FAS
- Exclusions from PPS
- Number of subjects who died in hospital up to Day 5
- Number of subjects who were discharged up to Day 5

16 Demographics and Other Baseline Characteristics

All data recorded at baseline will be summarized by treatment group. Since it is a randomised study, no statistical tests will be performed to compare these data between the groups.

Summaries will be presented for FAS and PPS separately.

The following baseline information will be presented:

- Age, (y)
- Sex
- Weight (kg)
- NEWS score at ED presentation
- SOFA score at d1, and the constituting components, i.e.
 - GCS score
 - Use of vasopressors and MAP
 - Bilirubin (mg/dL)
 - Creatinin (mL/day)
 - Platelets
 - $\text{PaO}_2/\text{FiO}_2$ ratio
- Sepsis or septic shock (defined as (MAP <70 or use of vasoactive agents) and (lactate>2 mmol/L))
- Sepsis etiology, No (%)
 - Respiratory
 - Gastro-intestinal
 - Urinary
 - Skin or soft tissue
 - Catheter
 - Other/unknown
- Physiological variables (d1)
 - Serum creatinine, mg/d
 - Procalcitonin, ng/ml
 - CRP, mg/l
 - Sodium, mmol/l
 - Lactate, mmol/l
- Interventions during admission, Y/N + # days
 - Mechanical ventilation
 - Vasopressors
 - Renal replacement therapy
- IV fluids
 - Total of IV fluids administered at d1
- Time from ED presentation to 1st dose of Vitamin C
 Time to 1st antibiotic

Mean (SD) and median (IQR) will be reported for all continuous variables.

17 Primary and Secondary Endpoints

All used tests are two-sided and alpha is set at 0.05 for the primary as well as for the secondary outcomes.

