The required sample size is calculated to detect with at least 80% power a difference in average post-baseline patient SOFA score (calculated over days 2 to 5), based on a constrained longitudinal data analysis model with alpha set at 0.05 (Liang and Zeger, 2000). The power is calculated using an approach presented by Stroup (Stroup, 1999). In the cLDA, both the baseline and post-baseline value are modeled as dependent variables, as opposed to a (longitudinal) ANCOVA model in which the baseline value is included as a covariate. Although the baseline measure is included in the response vector in cLDA, the true baseline means are constrained to be the same for different treatment groups due to randomization, and this analysis provides an adjustment for the observed baseline difference in estimating the treatment effects. Since the randomization is performed within center, considering center as an effect in the analysis has no impact on the sample size. Patients who die within the time period of 5 days receive the worst outcome (highest SOFA score) starting at the day of death. Based on the cLDA model, 126 patients per group (252 patients in total) are needed to detect with at least 80% power a difference between the control and intervention group of 1 in average post- baseline SOFA score. A standard deviation of the SOFA score equal to 3.5 and a correlation between the time points equal to 0.5 was assumed. These were conservative estimates, derived from reported information in two studies (Fowler et al, 2019; Fujii et al. 2020). 2.5%, 5%, 10% and 15% missing values are assumed on d2, d3, d4 and d5, respectively (combination of dropout and mortality). However, the sample size will be increased to 150 patients per group to anticipate a larger variability due to the imputation of one or more maximal SOFA scores for deceased patients.

7 Analysis Populations

The following analysis sets will be of interest:

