if PaO2FiO2c=1 then SOFA=SOFA+0;
if PaO2FiO2c=2 then SOFA=SOFA+1;
if PaO2FiO2c=3 then SOFA=SOFA+2;
if PaO2FiO2c=4 then SOFA=SOFA+2;
if PaO2FiO2c=5 then SOFA=SOFA+3;
if PaO2FiO2c=6 then SOFA=SOFA+4;

if O2FiO2c=1 then SOFA=SOFA+0;
if O2FiO2c=2 then SOFA=SOFA+1;
if O2FiO2c=3 then SOFA=SOFA+2;
if O2FiO2c=4 then SOFA=SOFA+3;
if O2FiO2c=5 then SOFA=SOFA+4;

*deceased patients receive maximal score from the day of death on;
if Fudate>=Deathdate>.z then SOFA=24;

*when lab analysis is forgotten, SOFA is put on missing;
if nolab_analreas_day=2 then SOFA=.;

*when info is missing if a lab analysis was performed, SOFA is put on missing;
if lab_anal_day<=.z then SOFA=.;

*if no lab analysis is performed and there is no information on the reason of a
missing lab analysis, SOFA is put on missing;
if lab_anal_day=0 and nolab_analreas_day not in (1,2) then SOFA=.;
```

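### The death rule is not confined to post-baseline days, so a death on day 1 overwrites the measured baseline SOFA with 24 in a model that forces equal baselines

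*SAP*

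**What the plan says.** - **Day 1.** Section 8.2: "Day 1 is defined as the day of randomization". Section 7.3 shows that at least one dose is planned on that day. Section 16 lists the day-1 SOFA among the baseline data.
- **Model.** Section 17.1 fits a cLDA to five daily measurements. Section 6 explains that "the true baseline means are constrained to be the same for different treatment groups due to randomization".
- **Death rule.** Section 9 assigns 24 to deaths within the five days, "starting at the day of death (even if a SOFA score is available at the day of death". In Addendum 1 this is "if Fudate>=Deathdate>.z then SOFA=24". Neither has a condition on the day.
- **Lab rule.** Where a required lab value is missing, Section 9 carries the previous value forward. For day 1: "In rare cases where this happened at d1, the value of d2 will be used for the calculation of the SOFA score".
- **Subgroup.** Section 14 splits patients at a baseline SOFA of 6. No baseline SOFA other than the day-1 score is defined.
- **Scale.** Section 17.1 makes the inverse hyperbolic sine (asinh) scale primary and the raw scale a sensitivity analysis.

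**The concern.** Constraining the baseline means is justified because randomisation makes the arms equal before treatment. That holds only if nothing after randomisation enters the baseline value. Both Section 9 rules let it in. The death rule overwrites even a measured score, and the lab rule imports a value from the day after dosing was due to start.

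The model reads an excess of 24s at day 1 in one arm as chance baseline imbalance and corrects the day 2–5 contrast for it. The rule meant to penalise death thus partly cancels its own penalty for the earliest deaths. A patient with a measured score below 6 who dies on day 1 also moves to the ≥6 subgroup because of the outcome.

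**Working it through.** **The plan's own figure.** On sample size, Section 6 says "126 patients per group (252 patients in total) are needed to detect with at least 80% power"; the target is 1 SOFA point in the day 2–5 mean. Its inputs are SD 3.5, correlation 0.5 and 2.5/5/10/15% missing on days 2–5. Section 17 sets two-sided alpha at 0.05. With compound symmetry, monotone missingness and separate baseline means per arm, 126 per group gives power 0.802, so the figure reproduces. With the constrained baseline that the SAP describes, 78 per group would suffice, and 150 gives power 0.974. The stated number is therefore conservative. That is a separate matter, but the same inputs drive the check below.

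**Mechanism.** With complete data the cLDA contrast is close to

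estimate = D(post) − β × D(day 1),

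where D is the difference between arms and β is the slope of the day 2–5 mean on day 1. Under the SAP's correlation β = 0.5. It rises to about 0.55–0.68 (raw scale) when some patients carry 24 on all five days.

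**Death route, by hand.** If k patients in one arm of n die on day 1 with measured score b, the rule shifts D(day 1) by k(24 − b)/n. The SAP gives neither k nor b. Assume k = 3, b = 12, n = 150:
- Raw: 3 × 12/150 = 0.24. Times β of about 0.6, this gives a loss of about 0.14 points.
- asinh: asinh(24) − asinh(12) = 3.872 − 3.180 = 0.692, and 3 × 0.692/150 = 0.0138. Times β of about 0.56, the loss is about 0.008.

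**Death route, simulated.** Assumptions: 150 per arm; daily means 6/5/4.5/4/3.5; SD 3.5; correlation 0.5; scores rounded and limited to 0–23; no missing data; all k deaths in one arm with b = 12 and 24 on days 2–5; a further 0.6-point effect in the same direction on days 2–5; adjustment for day 1 by ANCOVA; 2,500 replicates.

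| k | Raw: measured baseline kept → set to 24 | Loss | asinh: kept → set to 24 | Loss |
|---|---|---|---|---|
| 1 | 0.65 → 0.61 | 6% | 0.157 → 0.154 | 2% |
| 3 | 0.86 → 0.71 | 17% | 0.176 → 0.168 | 4% |
| 5 | 1.05 → 0.78 | 26% | 0.192 → 0.179 | 7% |

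Without the further effect, so that day-1 deaths are the whole difference, 3 deaths give 0.34 → 0.19 and 5 give 0.54 → 0.26 on the raw scale, a loss of 40–50%. On the asinh scale the loss is roughly 30% (24–34% across repeated runs, because the effect itself is so small).

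**Sensitivity to b.** If patients who die on day 1 had an average measured score (6 or 8) instead of 12, the gap to 24 is wider. For a total effect near 1 point:
- a 1-percentage-point difference in day-1 deaths loses 9–12% raw and 3–4% asinh;
- a 2-point difference loses 18–24% raw and 8–9% asinh;
- if a 2% versus 0% split were the whole effect, 61% raw and 48–53% asinh would go.

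**When nothing is lost.** Day-1 deaths of 1% in each arm with a 1-point effect: no loss. Deaths of 2% in each arm and no treatment effect: estimate about 0.

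**Lab route.** Loss = β × share back-filled × effect on the filled component. For a 1-point effect on that component: 0.5 × 0.02 × 1 = 0.010 and 0.5 × 0.05 × 1 = 0.025, or 1% and 2.5% of a 1-point treatment effect. With a 0.33-point effect and 5% back-filled: 0.5 × 0.05 × 0.33 = 0.008.

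**Program order.** In Addendum 1 the statements that set SOFA to missing come after the 24 is assigned. If lab status is blank once a patient has died, the 24s on days 2–5 become missing. The contrast is then not attenuated through day 1, but the death drops out of the primary comparison, contrary to Section 9.

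**The case against.** The strongest reply is that the harm is conditional and probably small. It needs unequal deaths on the calendar day of randomisation, or a treatment effect on day-2 labs among back-filled patients. The SAP counts neither and calls the second rare. The primary scale compresses a jump to 24. Section 9 promises frequency tables for each imputation setting, and Section 15 reports deaths up to day 5 by arm, so affected cases should be largely visible. The program variable is labelled a follow-up date, so perhaps baseline records were never meant to pass through that line.

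Most of this stands as to size. It does not rescue the rule. The tables would show how often it was applied but would not correct the estimate, and no sensitivity analysis with an untouched baseline is planned. The Section 9 list covers day 1 elsewhere (the lab rule), and no separate day-1 calculation is given.

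Some stronger readings are tempting but unsupported:
- *That a treatment effect is adjusted away as a matter of course.* It is not. Without day-1 deaths the death route vanishes.
- *That 40–50% of the effect is at risk.* That needs day-1 deaths to be essentially the whole effect, and it is on the sensitivity scale.
- *That false-positive risk rises.* With no effect and equal day-1 deaths the estimate centres on zero.
- *That every day-1 SOFA is post-dose.* The SAP does not say when on day 1 the score is taken.
- *That subgroups are widely reshuffled.* A patient with a measured score of 12 is already in the ≥6 group. Only a day-1 death with a measured score below 6 moves.

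**Conclusion.** The point holds as a specification error with a conditional consequence. Read as written, text and program both put the outcome into the baseline for anyone who dies on day 1, and the lab rule does so on a smaller scale.

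The contribution of unevenly distributed day-1 deaths is shrunk toward no effect: by about 2–7% of the total effect on the primary scale and 6–26% on the raw scale, for 1 to 5 one-sided deaths in arms of 150, b = 12 and a total effect of about 0.65–1.05 points. Somewhat larger losses follow if the measured scores were lower. Should day-1 deaths run against the rest of the effect, the same shrinkage would favour the arm with more of them.

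Power is not the main issue. For a true 1-point effect at 150 per group it falls from 0.974 to about 0.94 after a 10% loss and about 0.87 after a 21% loss. These rest on SD 3.5, compound symmetry and the raw scale. All magnitudes depend on assumed counts.

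**What to change.** 1. Section 9: state that the death rule applies to days 2–5 only. A patient who dies on day 1 keeps the measured day-1 SOFA as baseline (missing if there is none) and scores 24 on days 2–5. The Section 14 subgroup then uses that measured score.
2. Addendum 1: add a day-greater-than-1 condition to the line that assigns 24, and move it below the statements that set SOFA to missing. The day condition alone is not enough, because blank lab status after death would still erase the 24s.
3. Section 9: do not use a day-2 lab for day 1. Use a pre-dose value if one was recorded; otherwise leave the day-1 SOFA missing. The cLDA treats day 1 as a response and accommodates this.
4. Report by arm the number of day-1 deaths and day-1 back-fills. If analyses have already been run, these counts show whether refitting can matter.

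The cost is a few sentences, one condition and one moved line in the program, and possibly a few missing baselines.
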